5.2.2 Inclusion Criteria

- Premenopausal women, aged 18-51 years
- Expressed desire for compliance-independent contraception
- No current pregnancy or anticipated desire for childbearing within 3 years of study enrollment and ESI insertion
- Agreement to participate in all study related procedures and evaluations as documented by a signed informed consent (see appendix)

5.2.3 Exclusion criteria

- Current or prior use of ESI
- Current long-term use of Doxycycline for other indications
- Known structural uterine abnormalities such as polyp, submucosal leiomyoma
- Prior permanent sterilization or endometrial ablation
- Pregnancy or desire for childbearing within 3 years
- Contraindications to or intolerance of etonogestrel
- Allergy to or intolerance of Doxycycline
- Inability or unwillingness to complete study related procedures and evaluations, and document this agreement by signing the informed consent

Patient Process Chart

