Matrix metalloproteinases cause endometrial fragility, irregular vessel breakdown, influx of leukocytes, and bleeding. [15, 16] Tetracyclines inhibit matrix metalloproteinase activity independent of their antimicrobial action, with doxycycline being the most potent inhibitor among the tetracyclines [17, 18]. Doxycycline also treats Chlamydia and Ureaplasma infection, which may cause chronic endometritis that presents as abnormal uterine bleeding [19]. A pilot study by Weisberg [21] reported a 50% reduction in ESI-related bleeding duration with doxycycline for 5 days but no long-term improvement and no improvement over placebo in a follow-up study [22]. Doxycycline anti-inflammatory effects are dependent on dose and treatment duration *in vitro* [20] thus supporting a longer therapy course. Clinically there is no precedent for increasing dose beyond 100 mg BID. While there is a clinical precedent for using 10 days of treatment, there is not for 5 days of use. This length of administration was likely used in the Weisberg studies(21,22) for blinding purposes [21,22].In our retrospective cohort (N=9), 10 day course of Doxycycline resulted in bleeding improvement and method continuation in 66% of patients who reported unacceptable bleeding.[3,7] Of 36 untreated patients, 25 (70%) requested early ESI removal.[7]

The published experience with Doxycycline in the treatment of unacceptable bleeding associated with ESI is limited to small, retrospective studies. The validation and subsequent clinical implementation of an evidence-based cost-effective treatment is likely to dramatically increase the acceptability and continuation rates of ESI.

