5.2.1 Patient selection

After appropriate IRB approval, ESI users aged 18-51 years old who meet the inclusion and exclusion criteria, and sign a written consent will be **enrolled in the study at the time of ESI insertion**. Every effort will be made to insert ESI on the same day as consent unless medically contraindicated. They will complete a prospective symptom diary from date of ESI insertion. All patients will be contacted by study personnel 13 weeks after enrollment and queried as to the presence of unacceptable bleeding. Bleeding concerns will be objectively assessed using a modification of the Pictorial Blood Loss Assessment Chart (PBLAC) [27]. Patient-initiated contact in with bleeding concerns at any time after 13 weeks post ESI insertion will result in enrollment and randomization at the time of contact. **The basis for randomized treatment will be whether or not the bleeding is “unacceptable” to the patient. This is inherently subjective, but constitutes the basis for most removal requests.** Patients who report unacceptable bleeding at 13 weeks post-ESI insertion, and those who call with bleeding concerns after 13 weeks post ESI insertion, will be randomized into two groups (Doxycycline or placebo). Patients who do not report unacceptable bleeding will continue to complete diaries and may be eligible for randomized treatment if unacceptable bleeding develops. Patients will receive diaries sufficient for completion of the study with instructions to contact study personnel if more diaries are needed or if diaries are lost. Patients and investigators will be blinded to the group assignment as well as the study coordinator who will be responsible dispensing of appropriate study medication by the pharmacy.

Patients who continue to have unacceptable bleeding after 4 weeks post-randomized treatment and wish to have secondary treatment will be treated with Doxycycline. Secondary treatment will not be blinded. Rates of unacceptable bleeding and patient satisfaction scores at 26 weeks post-randomized treatment in remaining study participants will be calculated.

[figure not shown]

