5.3 Measurements of Study Variables

5.3.1 Study Process

a. Enrollment

Subjects who meet the eligibility criteria will be required to sign an informed consent form and HIPAA authorization prior to enrollment. Subjects will receive identification numbers at this time and will be considered enrolled into the study. Patient demographic characteristics, prior contraceptive method, postpartum and breastfeeding status will be recorded. All subjects will undergo a history and physical examination including pelvic examination, height and weight if this was not done within an age-appropriate interval. A baseline BMI will be calculated. A Pap test using ThinPrep[®] will be obtained if none has been taken in the preceding 12 months. A retrospective symptom diary to date of ESI insertion and prospective symptom diaries for the duration of the study will be provided to the patient with instructions to contact study personnel if materials are lost or more are needed.

b. Randomization

Patients enrolled in the study at the time of ESI insertion who either report unacceptable bleeding when contacted by study personnel at 13 weeks post-ESI insertion or self-report unacceptable bleeding after 13 weeks post ESI insertion will be offered randomization to placebo or Doxycycline. Randomization will be done with stratification based on: age (< 30 years, ≥ 30 years), postpartum status and body mass index (BMI < 30, BMI ≥ 30). The randomization will be performed using a dynamic allocation approach based on the Pocock-Simon method to ensure a balance in the treatment groups across the stratification levels. The randomization assignment for each patient will be obtained upon entering the patient's stratification levels into a web-based application created and supported by the Division of Biomedical Statistics and Informatics. Investigators and patients will be blinded to group assignment. For this reason, all pills will be made to look identical. **Enrollment of new patients will continue until approximately 100 patients are randomized (50 in each group).** Additional patients will need to be enrolled given the lower than expected reported unacceptable bleeding rates.

c. Placebo group

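### The background-drug exclusion names only long-term doxycycline and is not re-checked at randomization, so women on a long-term tetracycline can be randomized and could dilute the contrast

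*Combined protocol and SAP*

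**What the plan says.** Section 5.2.3 has one criterion on background drug use: "Current long-term use of Doxycycline for other indications". It names one drug, and only current, long-term use of it. Neither the inclusion nor the exclusion criteria mention any other tetracycline.

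Section 4.0 gives the reason for expecting an effect: "Tetracyclines inhibit matrix metalloproteinase activity independent of their antimicrobial action, with doxycycline being the most potent inhibitor among the tetracyclines". The same paragraph adds that "Doxycycline anti-inflammatory effects are dependent on dose and treatment duration", citing in vitro work.

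On timing, section 5.2.1 has women "enrolled in the study at the time of ESI insertion" once they meet the criteria. Section 5.3.1b offers randomization later, to women who "report unacceptable bleeding when contacted by study personnel at 13 weeks post-ESI insertion" or who report it themselves after that point. It describes no second look at the exclusion criteria.

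On data, section 5.3.1a states: "Patient demographic characteristics, prior contraceptive method, postpartum and breastfeeding status will be recorded". A history and examination are also planned, subject to when they were last done, but concomitant medication is not among the listed items. Section 5.4.2 plans models adjusted for potential confounders and does not name them.

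**The concern.** The existing criterion shows that the sponsor wants to keep background exposure to the study drug out of the comparison. The plan's own rationale places the enzyme inhibition in the class and calls doxycycline its strongest member, not its only one. On that reasoning the criterion stops short of its purpose.

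The timing adds a second opening, and the more concrete one. A criterion satisfied at insertion says nothing about drugs started during the next 13 or more weeks. As written, even long-term doxycycline begun in that interval would not bar randomization.

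At stake is the difference between arms in need for additional treatment, the primary endpoint. If some placebo women have part of the studied effect from another source, or if some women in both arms are already unresponsive to the class, the expected difference shrinks. Because medication is not a listed data item, a null or weak result could not readily be examined for this explanation.

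**Working it through.** **Inputs from section 5.4.1:** 50 women per arm; need for additional treatment 44% on doxycycline and 80% on placebo; two-sided chi-square test at 0.05; stated power above 90%.

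**Assumed input:** the share *f* of randomized women on a background long-term tetracycline. The documents give no figure, so a range is shown.

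**Step 1, the plan's own figure.** Power is the sum, over all pairs of event counts (i on placebo, j on doxycycline), of the two binomial probabilities wherever |i − j|/50 ÷ √(p̄(1 − p̄) × 2/50) exceeds 1.96, with p̄ = (i + j)/100. At 80% against 44% this gives 97.0%. The stated figure is reproduced.

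**Step 2, full-effect model, taken as the upper bound.** Placebo women on a background tetracycline are given the doxycycline rate, and the doxycycline arm stays at 44%:

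placebo rate = 0.80 − f × (0.80 − 0.44) = 0.80 − 0.36f

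| f | Expected placebo users of 50 | Placebo rate | Difference (points) | Power |
|---|---|---|---|---|
| 0% | 0 | 80.0% | 36.0 | 97.0% |
| 2% | 1 | 79.3% | 35.3 | 96.3% |
| 5% | 2.5 | 78.2% | 34.2 | 95.1% |
| 10% | 5 | 76.4% | 32.4 | 92.6% |
| 15% | 7.5 | 74.6% | 30.6 | 89.3% |

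The usual normal-approximation formula puts the 90% crossing at f = 13.4%, or 0.134 × 50 = 6.7 placebo women. Exact enumeration puts it slightly higher, between 10% and 15%. About 13% is the cautious statement.

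**Step 3, non-responder model.** A woman randomized while on such a drug has bled unacceptably despite it. Suppose these women fail at 80% in both arms:

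doxycycline rate = 0.44 + 0.36f

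At 5% this is 45.8%, with power 95.4%. At 10% it is 47.6%, with power 93.3%.

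**Step 4, no-dilution case.** If the background drug leaves the placebo rate at 80% and added doxycycline still brings the rate to 44%, the difference stays at 36 points and power at 97.0% for any f.

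**The case against.** The strongest reply is that nothing in the documents shows that any participant takes a tetracycline. A reader might infer that the contrast *is* diluted. The text supports only that it could be.

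A reader might also infer that placebo becomes an active comparator for such women. Section 4.0 does not go that far. It ranks doxycycline as the most potent of the class, describes its effect as dependent on dose and duration, and reports that a 5-day doxycycline course did not beat placebo in a follow-up study. It does not say that another drug of the class, as taken for another indication, changes implant bleeding. Women also reach randomization only by reporting unacceptable bleeding, so a background drug still being taken has not prevented it. Crediting that drug with the full planned effect is a ceiling, not an expectation.

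Nor can one say that the bias always runs toward no difference: step 4 is a possible case with none.

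Finally, no stated figure fails at low use, and adjustment for confounders is already planned.

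Most of this stands and sets the size of the point. It does not close the gap. The criterion is still narrower than the rationale, no re-check is described, and the adjustment plan cannot use a variable that is not listed for collection.

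**Conclusion.** The point holds as a minor gap in eligibility and data collection. The exclusion is narrower than the plan's own account of the mechanism, and it is applied only at insertion. Women on a long-term tetracycline can therefore be randomized, which could dilute the primary contrast.

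The size depends on an assumed share and an assumed effect. Under the ceiling model the loss is 0.7 points of power at 2% use (97.0 − 96.3), 1.9 at 5% (97.0 − 95.1) and 4.4 at 10% (97.0 − 92.6). It is 1.6 and 3.7 points at 5% and 10% if users fail in both arms, and nil if added doxycycline works as planned and the background drug does not lower the placebo rate. The claim of more than 90% power is not broken below about 13% use. The documents do not support calling the primary comparison flawed.

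A reader might also set "Contraindications to or intolerance of etonogestrel" beside "Allergy to or intolerance of Doxycycline" and infer a safety gap. The two drugs need not have parallel wording, the documents list no doxycycline contraindication that the criteria miss, and the matter has no bearing on dilution. It is not part of this point.

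**What to change.** 1. In section 5.2.3, insert 'or any other tetracycline' after doxycycline in the long-term-use line.
2. In section 5.3.1b, state that this line is applied again when randomization is offered, and record the answer.
3. For women already randomized, flag long-term tetracycline use present before randomization from the medical record, before treatment codes are opened. Section 5.2 describes the electronic records as easy to abstract. Repeat the primary chi-square comparison without the flagged women as a sensitivity analysis. Use only pre-randomization status: drug use begun afterwards may itself reflect the assigned treatment, and excluding on it would undo the randomization.

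The cost is a phrase in the criteria, one question or chart check per woman at randomization, and one extra analysis. The downside is that a few women become ineligible for randomization. With few flagged women, the sensitivity analysis will probably change little; its value is in showing that background use does not explain the result.

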5.3 Measurements of Study Variables

5.3.1 Study Process

a. Enrollment

Subjects who meet the eligibility criteria will be required to sign an informed consent form and HIPAA authorization prior to enrollment. Subjects will receive identification numbers at this time and will be considered enrolled into the study. Patient demographic characteristics, prior contraceptive method, postpartum and breastfeeding status will be recorded. All subjects will undergo a history and physical examination including pelvic examination, height and weight if this was not done within an age-appropriate interval. A baseline BMI will be calculated. A Pap test using ThinPrep[®] will be obtained if none has been taken in the preceding 12 months. A retrospective symptom diary to date of ESI insertion and prospective symptom diaries for the duration of the study will be provided to the patient with instructions to contact study personnel if materials are lost or more are needed.

b. Randomization

Patients enrolled in the study at the time of ESI insertion who either report unacceptable bleeding when contacted by study personnel at 13 weeks post-ESI insertion or self-report unacceptable bleeding after 13 weeks post ESI insertion will be offered randomization to placebo or Doxycycline. Randomization will be done with stratification based on: age (< 30 years, ≥ 30 years), postpartum status and body mass index (BMI < 30, BMI ≥ 30). The randomization will be performed using a dynamic allocation approach based on the Pocock-Simon method to ensure a balance in the treatment groups across the stratification levels. The randomization assignment for each patient will be obtained upon entering the patient's stratification levels into a web-based application created and supported by the Division of Biomedical Statistics and Informatics. Investigators and patients will be blinded to group assignment. For this reason, all pills will be made to look identical. **Enrollment of new patients will continue until approximately 100 patients are randomized (50 in each group).** Additional patients will need to be enrolled given the lower than expected reported unacceptable bleeding rates.

c. Placebo group

If a patient reports bleeding concerns as described in section 5.2.1 and is randomized to the placebo group, she will be given a pill bottle containing placebo made to look identical to treatment to be taken twice daily for 10 days. Patient and investigators will be blinded as to group assignment.

d. Doxycycline group

If patient has bleeding concerns determined in section 5.2.1 and is randomized to the Doxycycline group, she will be given a pill bottle containing Doxycycline 100 mg to be taken twice daily for 10 days. Patient and investigators will be blinded as to group assignment. Patients who experience unacceptable bleeding but are not bleeding at the time of study personnel contact will be instructed to call back if unacceptable bleeding recurs for randomization to treatment or placebo.

e. Treatment compliance process

Pill counts at the end of each treatment course will be performed to assess patient compliance with treatment. A pill diary given to patients at the time of randomization will provide temporal correlation between treatment initiation and bleeding symptoms.

f. Symptom recording

Upon enrollment and ESI insertion, patients will begin a weekly prospective symptom diary in order to self-assess bleeding and additional symptoms for a **total of 39 weeks from study enrollment**. A modification of the PBLAC where 1= no bleeding, 2=spotting requiring 1-2 panty-liners per 24 hours only, 3= bleeding requiring 1-3 tampons/pads in 24 hours, 4=bleeding requiring 4-6 tampons/pads per 24 hours, and 5=bleeding requiring >6 tampons/pads per 24 hours will be utilized for bleeding recording.[27] Bleeding diaries will be collected every 13 weeks and completion will be required for continued enrollment in the study and receipt of remuneration after every 13 week interval. Patients will also record any other associated symptoms such as headache, mood changes, acne and intolerance to treatment detailed in sections 6.2.2 and 6.2.3. Prospective symptom diary can be captured on a paper formate or via Mayo Clinic website RED Cap.

A bleeding episode is defined by the WHO as any set of one or more bleeding days (either consecutive or separated by only one bleeding-free day) bounded at each end by two or more bleeding-free days. **The bleeding pattern will be analyzed within each 13-week reference period** and categorized into 6 groups [4, 13, 14]:

- Amenorrhea (no bleeding during the reference period),
- Infrequent bleeding (fewer than 3 bleeding episodes),
- Normal bleeding frequency (3-5 bleeding episodes).
- Frequent bleeding (more than 5 bleeding episodes),
- Prolonged bleeding (1 or more bleeding episodes lasting 14 days or more)

Subgroup analysis may provide additional insight into the efficacy of treatment for various bleeding patterns.

g. Patient satisfaction surveys

Patients will be asked to fill out short satisfaction surveys at randomization measuring satisfaction prior to any treatment, and at 13 and 26 weeks post randomization (see appendix). If patient has their ESI removed prior to 26 weeks post randomization, she will be given a final satisfaction survey at removal. Patient satisfaction surveys will be recorded on a paper formate or via Mayo Clinic website RED Cap.

Patients will rate their satisfaction with a) ESI and b) bleeding with ESI on a 5-point Likert scale ranging from very satisfied to very dissatisfied. If patient has ESI removed prior to 26 weeks post-study enrollment, she will be given a final satisfaction survey at removal.

h. Treatment issues

At enrollment, patients will be provided with a contact number allowing them to reach study personnel at all times with concerns. Instructions will be provided for instances of drug intolerance/allergy, heavy bleeding or other ESI related issues and clinical appointments for evaluation scheduled as needed.

i. Secondary Treatment

If a patient reports unacceptable bleeding at >4 weeks post randomization to treatment or placebo, study participation will be recorded as **need for additional treatment, and will represent the primary endpoint**. If she wishes to have secondary treatment, she will be treated with Doxycycline. Treatment will be limited to two interventions per 13 week

interval to allow for assessment of efficacy of each course of Doxycycline. Rates of unacceptable bleeding in all patients remaining in the study at 26 weeks post-randomization will be calculated and participation in the study will end. If patients request ESI removal at any time during the study after randomly assigned treatment, study participation will be recorded as a **removal**. Method satisfaction will be assessed at removal and study participation will end. Patients will be provided with alternative contraception of choice at their expense. **Need for additional treatment at >4 weeks post-randomized treatment will represent the primary endpoint.** Satisfaction with ESI at randomization, and 13 and 26 weeks post randomization, and method continuation at 26 weeks post-randomization represent the secondary endpoints.

j. Post-treatment Followup

All patients will be contacted by study personnel at 26 weeks (\pm 2 weeks) post-randomization for final satisfaction survey and weight. Study completion BMI will be calculated. All diaries will be collected for analysis and patients will receive remuneration. When all patients complete the study, the data will be unblinded for analysis.

k. Special Considerations

If patients receive randomized treatment toward the end of the 39 week study interval (rather than at about 13 weeks post ESI insertion), post-treatment data for at least 13 weeks will be collected for a maximum study length of 52 weeks post-ESI insertion.

l. Additional testing

Additional laboratory testing or imaging for heavy or unusual bleeding will be individualized as clinically indicated.

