Patients will be analyzed according to their randomized treatment arm. All calculated p-values will be two-sided and p-values less than 0.05 will be considered statistically significant. Analyses will be performed using SAS software package (version 9.2). Comparisons of categorical endpoints (e.g. need for additional treatment, bleeding pattern based on the WHO classification, presence of adverse event(s), satisfaction survey questions) between the two arms will be evaluated using the chi-square test. Additional comparisons of these endpoints, adjusted for potential confounders, will be assessed by fitting separate logistic regression models. Time-to-event methodology (e.g. Kaplan-Meier method and Cox proportional hazards regression models) will be utilized for binary versions of these endpoints if patient follow-up becomes an issue and patients don't comply with the planned follow-up before completing the study. Poisson regression models will be used to compare the diary responses between the treatment arms. In the Poisson model, the endpoint will be the number of bleeding and spotting days per patient (and likewise the number of days with additional symptoms), offset by the total days of diary follow-up per patient. Ninety-five percent confidence intervals (95% CI) will be constructed around the estimates for method continuation and satisfaction.

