8.2 Limitation relating to recall bias

We expect some recall bias and late entries to the symptom diary.

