10.1.1 Remuneration

Patients will receive \$25 after each interval of 13 weeks for completion of prospective symptom diary (and pill diary if applicable) and satisfaction survey. Patients who discontinue study participation prior to completion of each 13 week set of diaries/satisfaction survey, those who do not turn in all diaries/satisfaction survey or turn in incomplete diaries/satisfaction survey will not receive this remuneration. Patients who complete the study will receive \$50.00 upon receipt of final set of diaries, satisfaction survey and study coordinator clinic visit.

[name] Investigator

- Proposal and associated material preparation
- IRB approval process
- patient consent, patient satisfaction surveys, bleeding diary preparation
- study marketing within Mayo and to MHS sites
- training and oversight of study personnel, troubleshooting
- clinical appointments for concerns
- progress report preparation
- data analysis
- manuscript preparation/submission/revision

[name]

- study marketing within Mayo and to MHS sites
- training and oversight of study personnel, troubleshooting
- clinical appointments for concerns

Study coordinator

- Patient Consent & Enrollment
- (available on-call for routine GYN clinic, scheduled for women responding to advertising)
- Available for phone contact by subjects throughout the study (triage of subject concerns)
- Phone contacts at 13 weeks for all subjects (450+)
- Clinic visits for “unacceptable bleeding” and randomization (150+)
- Phone contact at 26 weeks for all subjects
- Clinic visit at 39 weeks for all subjects

- Potential additional post-39 week phone contact for limited # subjects with late randomization
- Baseline - Consent form copying & scanning
- Baseline – data collection / case report form completion
- Subject education re: diary completion, study plan, subject responsibilities
- Collection of subject diaries at 13 – 26 – 39 weeks
- Assessing treatment compliance for randomized and secondary treatment
- Satisfaction surveys at 13 – 26 – 39 weeks
- Documentation of study participation, randomization, and follow-up in medical record
- Data entry into electronic database (clinical data, diary data, satisfaction survey data)
- Maintain subject binders / folders (150+ complex and 300+ simple)
- Organize and develop system for follow-up visits and phone calls
- Scheduling of follow-up visits (prefer to have support of the PAC office)
- Remuneration for all subjects
- Consent form development

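### Diary completion is a condition of staying enrolled, even after randomization, and nothing provides for primary-endpoint follow-up of women removed under that rule

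*Combined protocol and SAP*

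**What the plan says.** Section 5.3.1.f attaches two consequences to the diary, continued enrollment and payment: "Bleeding diaries will be collected every 13 weeks and completion will be required for continued enrollment in the study", and the same sentence goes on to make payment depend on it too. It does not define completion and does not separate women before randomization from women after it.

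Section 10.1.1 treats incomplete diaries as a payment matter only: women who "turn in incomplete diaries/satisfaction survey will not receive this remuneration". Its coordinator task list gives the schedule as "Collection of subject diaries at 13 – 26 – 39 weeks" without stating the time origin.

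The primary endpoint is described in more than one way. Section 5.3.1.i rests it on the woman's own report: "If a patient reports unacceptable bleeding at >4 weeks post randomization to treatment or placebo", she is recorded as needing additional treatment. Section 2.0, under aim 1, says that the endpoint is determined from completed symptom recording by 13 weeks. Section 5.3.2.A names both the rate of unacceptable bleeding and the weekly diary.

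On analysis, section 5.4.2 says "Patients will be analyzed according to their randomized treatment arm". It gives no rule for a missing primary outcome. It mentions Kaplan-Meier and Cox methods if follow-up becomes a problem, with no trigger. Section 8.2 adds: "We expect some recall bias and late entries to the symptom diary".

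**The concern.** Keeping a diary after randomization is behaviour that treatment may influence. A woman whose bleeding has stopped may lose interest in recording it. One who is still bleeding, dissatisfied or unwell on the tablets may give up on it. If an incomplete diary ends enrollment, the women left for analysis are partly selected by how they fared, and the selection can differ between arms. That works against analysis by randomized arm.

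Such a loss would often be avoidable. Under the section 5.3.1.i definition the outcome is something the woman tells study staff, so a phone call could supply it after the diary has lapsed. The plan does not require that call for women removed under the diary rule. The Kaplan-Meier and Cox fallback would not cure this, because it assumes that censoring is unrelated to outcome, which is the assumption in doubt.

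**Working it through.** **1. The plan's own power figure.** Section 5.4.1 gives 50 per arm, 44% on doxycycline and 80% on placebo, a two-sided chi-square test at 0.05, and power above 90%. The formula is power = Φ{[d√n − 1.96·√(2·p̄·(1−p̄))] / √[p₁(1−p₁) + p₂(1−p₂)]}, with d = 0.36 and p̄ = 0.62.

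- n = 50: (2.546 − 1.345)/0.6375 = 1.88, so power is 97.0%. The stated figure is reproduced.

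**2. Power under equal loss unrelated to outcome (loss rates assumed).**

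| Loss per arm | n per arm | Power |
|---|---|---|
| 10% | 45 | 95.3% |
| 20% | 40 | 92.8% |
| 30% | 35 | 89.1% |

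Power falls below 90% at 36 or fewer per arm, which is about 28% loss. The reserve is wide.

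**3. Who is exposed.** Take collections at weeks 13, 26 and 39 from insertion. This origin is a reading of the section 10.1.1 task list. A woman randomized at week r, with r from 13 up to 26, is next checked at week 26, so 26 − r weeks of her 13-week window have been observed.

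- r = 13: 13 weeks. The window is closing and any reported event is already on record. Removal would mainly cost the 26-week satisfaction and continuation endpoints.
- r = 20: 6 of 13 weeks.
- r = 22: 4 weeks. A woman randomized between weeks 22 and 26 could be removed before a report would count, since section 5.3.1.i requires more than 4 weeks.

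The plan does not say how many women will be randomized late, but sections 5.3.1.b, 5.3.1.k and 7.1 all allow it.

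**4. Worst-case bounds on the difference.** Let a fraction m of primary outcomes be missing in each arm, and let the observed rates be 44% and 80%. The full-sample difference is 36(1 − m) from the observed women, plus or minus 100m from the missing ones:

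| m (assumed) | 36(1 − m) | Bounds (points) |
|---|---|---|
| 5% | 34.2 | 29.2 to 39.2 |
| 10% | 32.4 | 22.4 to 42.4 |
| 20% | 28.8 | 8.8 to 48.8 |

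The bounds are not centred on 36. At 20% they reach 27.2 points below it and 12.8 above.

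**5. A milder illustration.** Let the true difference be 36 points, with loss depending on outcome (fractions assumed).

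- Opposite patterns. Doxycycline loses 10% of events and 30% of non-events: 0.396/(0.396 + 0.392) = 50.3%. Placebo loses 30% of events and 10% of non-events: 0.56/(0.56 + 0.18) = 75.7%. The observed difference is 25.4 points.
- Placebo loses 30% of events and 10% of non-events, doxycycline 10% of all women: 75.7 − 44.0 = 31.7 points.
- The same loss on doxycycline instead, with placebo losing 10% of all women: 0.308/(0.308 + 0.504) = 37.9%, and 80.0 − 37.9 = 42.1 points.

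The bias can go either way.

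**The case against.** The best defence is that the sentence in section 5.3.1.f may be meant as an incentive more than a removal rule. Section 10.1.1 lists women who discontinue separately from those who hand in incomplete diaries, and there attaches only loss of payment. Lost diaries can be replaced. The Poisson model in section 5.4.2 is offset by days of diary follow-up, so it allows for unequal diaries. Section 5.3.1.j plans a contact for all patients at 26 weeks after randomization, and sections 5.3.1.k and 7.1 promise at least 13 weeks of data on women randomized late. All of this makes strict enforcement less likely. None of it cancels the sentence in 5.3.1.f or says that a woman no longer enrolled is still followed.

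A reader might infer that any woman who misses one diary is withdrawn and her primary outcome lost. The documents do not go that far. Completion is undefined, the check comes only at collection, and loss of the outcome is an inference from silence. The late entries expected in section 8.2 are also not the same as incomplete diaries.

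A reader might also infer that the primary endpoint needs no diary at all. That fits section 5.3.1.i but conflicts with section 2.0 and section 5.3.2.A.

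Finally, it is tempting to add that the rule turns away bleeding women before randomization. That cannot bias the comparison of arms, section 5.3.1.b states no diary condition for offering randomization, and section 7.1 attributes the rise to 470 enrolled to a lower rate of unacceptable bleeding. It is a secondary matter.

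**Conclusion.** The point holds as a design weakness that should be corrected. As written, section 5.3.1.f permits randomized women to be dropped for post-randomization behaviour, and no section keeps them in follow-up for the primary endpoint. The risk is bias in the primary comparison, concentrated in women randomized well after week 13. For those randomized near week 13 the cost is mainly to the 26-week endpoints.

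The size cannot be fixed from the documents, because neither a diary-failure rate nor the share of late randomizations is given. The bounds in step 4 apply to the fraction of primary outcomes actually missing. Equating that fraction with the diary-failure rate would overstate the problem, since many women would have had their outcome recorded before removal. The exposure by week also rests on collection being timed from insertion.

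**What to change.** - **Section 5.3.1.f:** delete completion as a condition of continued enrollment and keep it as a condition of remuneration only, consistent with section 10.1.1.
- **Follow-up:** state that every randomized woman, whatever her diary status, is contacted about need for additional treatment, removal and satisfaction at 13 and 26 weeks after randomization, unless she withdraws consent. For women randomized late, this applies as far as the 52-week maximum allows.
- **Primary endpoint:** reconcile sections 2.0 and 5.3.2.A with section 5.3.1.i, so that the endpoint rests on the woman's report of need for additional treatment and the diary is supporting data.
- **Section 5.4.2:** state how a primary outcome that is still missing will be analyzed.

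The cost is a short amendment. Section 5.3.1.g already plans a survey at 13 weeks after randomization and section 5.3.1.j a contact at 26 weeks. A few extra calls will be needed: a woman randomized at week 20 reaches 13 weeks at week 33, when the coordinator list has no routine contact. There will also be more partial diaries among the women retained.
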